MAINTAINING IMPLEMENTATION
THROUGH DYNAMIC ADAPTATIONS

MIDAS Quality Enhancement Research Initiative

Center for Clinical Management Research

[name]

[name]

[contact]

Official Title of Project: MIDAS Cluster Randomized Controlled Trial of Implementation Strategies to Optimize Use of Medications in VA Clinical Settings (MIDAS cRCT)

ClinicalTrials.gov ID: NCT05065502

Date: 09/24/2025

Please find the Study Protocol and Statistical Analysis Plan below. Since the creation of this document, the following changes have been made to the analysis plan:

- Data was collected through 18 months post-baseline rather than through 36 months due to time constraints.
- Instead of a patient-level dichotomous response over time, the differences between arms were modelled as a single outcome adjusting for the evidence-based practice (EBP) and the level of potentially inappropriate medications (PIMs) in the pre-period to address the large difference in PIMs between EBPs.
- After conducting additional testing of our algorithm for detecting CBTI sessions, we found the algorithm to be adequately sensitive to detecting *any* CBTI but not accurate for detecting the number of CBTI sessions (e.g., CBTI could often be mentioned in the context of a referral or some other ongoing treatment). Thus, the secondary outcome “Change in Mean Cognitive Behavioral Therapy for Insomnia (CBTI) Sessions Completed” could not be analyzed.
- We had originally planned for all CBTI sites to provide information regarding where in the medical records we could identify referrals. However, prior to launching the trial, we determined several of the sites' processes for referrals were not distinguishable as referrals vs. other forms of communication (e.g., adding a therapist as a cosigner to a note), making collection of this data impractical. Thus, we did not have sites collect referral criteria and the secondary outcome “Change in the Monthly Percentage of Patients Referred to Cognitive Behavioral Therapy for Insomnia (CBTI) Across Facilities” could not be analyzed.

A protocol paper for this project, titled “Maintaining Implementation through Dynamic Adaptations (MIDAS): protocol for a cluster-randomized trial of implementation strategies to optimize and sustain use of evidence-based practices in Veteran Health Administration (VHA) patients,” was published in May 2022.

[name], MS
Principal Investigator

Aims

Mixed methods analyses will be used to evaluate the following three aims:

1. *To compare the effectiveness of two implementation strategies (LEAP Quality Improvement Learning Program + Academic Detailing (AD) vs. AD alone) on potentially inappropriate medication use, using a pooled analysis of effects across three trials at 18 months, two years, and three years post-baseline at the clinic-level, based on monthly assessed data from 13-36 months;*
2. *To compare the effectiveness of the two implementation strategies on secondary outcomes specific to each trial at 18 months, two years, and three years post-baseline, based on monthly assessed data from 13 to 36 months; and*
3. *To explore the effects of implementation, provider behaviors and experiences, and context, on sustained improvements in potentially inappropriate medication use.*

Methods

Clinic Randomization

Within each trial, clinics will be randomized after assenting to participate (equivalent to enrollment). Clinics will be assigned to one of two arms by a statistician, stratified further by clinic type (medical center, community clinic, or Community Living Center) if needed to ensure partial balance between arms with respect to potential confounders associated with culture and complexities associated with clinic location [1,2].

Outcomes and Analyses

As part of a pooled analysis, we will compare the same two implementation strategies across all three EBPs and take a unified approach to implementation and evaluation across the trials. Table 1 shows MIDAS measures, data collection timeframe, and data sources. While a unified dichotomous outcome, i.e., potentially inappropriate medications, was identified for each trial to allow for the pooled analysis, each trial will also be analyzed individually (see Table 1).

Table 1: MIDAS Measures showing Data Sources and Timepoints by Aim

Aim	Type	Source
Aim 1: Primary outcome		
Service Outcomes		
Proportion of potentially inappropriate care	Quantitative	CDW administrative data
Aim 2: Secondary outcomes		
Service Outcomes		
VIONE Trial		
Potentially inappropriate use of proton pump inhibitors (PPIs), aspirin, and CNS active medications (e.g., muscle relaxants), analyzed one at a time	Quantitative	CDW administrative data
Monthly medication costs for all drugs	Quantitative	CDW administrative data
Number of pharmacist medication reviews	Quantitative	CDW administrative data

Aim	Type	Source
DOAC Trial		
Dashboard flags including potential mis-dosing, potential medication interactions, or concern for nonadherence	Quantitative	CDW administrative data
CBTI Trial		
Prevalence of any CBTI receipt	Quantitative	CBTI note templates completed by CBTI therapists
Patient Outcomes		
VIONE Trial		
Number of inappropriate medications by patient		CDW administrative data
Aim 3: Exploratory outcomes		
Employee Behavioral Outcomes		
Continuous Quality Improvement Assessment	Quantitative	LEAP and AD participants
Workgroup Cohesion & Engagement Scale	Quantitative	LEAP and AD participants
QI skill application	Quantitative	LEAP participants
Employee Experience		
Burnout	Quantitative	LEAP and AD participants
Best Places to Work	Quantitative	LEAP and AD participants
Process Evaluation		
Pragmatic Context Assessment Tool	Qualitative/ Quantitative	LEAP participants
Semi-structured interviews	Qualitative	Purposive sample of LEAP and AD participants
How often the provider uses the dashboard	Quantitative	CDW administrative data
Rates of new DOAC starts compared to warfarin starts	Quantitative	CDW administrative data
Fidelity	Qualitative/ Quantitative	Academic Detailer and Champion/LEAP Coaches
Provider satisfaction	Qualitative/ Quantitative	LEAP and AD participants
Intentions	Qualitative/ Quantitative	LEAP participants
Detailing visit documentation	Qualitative/ Quantitative	Academic Detailer and Champion
Coaching documentation	Qualitative/ Quantitative	LEAP Coaches
Semi-structured interviews	Qualitative	Purposive sample of LEAP and AD participants

Aim 1: Primary Outcomes and Pooled Analysis.

Although each trial will be conducted as an independent study, our primary aim is to compare across trials the effectiveness between the two implementation strategy arms in reducing potentially inappropriate medications during post-implementation period. To this end, we defined a unified primary outcome to allow us to combine the results *across* the three trials. The unified primary outcome will be operationalized based on a patient-level dichotomous response indicating potentially inappropriate

medication use (yes/no) among patients at-risk of potentially inappropriate medications, i.e., among those who may benefit from the specific EBP each month. The monthly patient-level potentially inappropriate medication use response will be summarized to clinic-level month-by-month percentage of potentially inappropriate use using administrative data from baseline to 36 months, with months 13-36 as the post-implementation follow-up period. Each trial-specific monthly data will be cross-sectional, i.e., different patients may be included in each month.

For *inappropriate polypharmacy*, the clinic-month outcome will be the proportion of patients who had medication possession (based on VA pharmacy fill data) of one or more medications from the AGS Beers criteria that are included on the VIONE PIMs dashboard [3] (numerator) among patients age 65 or older, not receiving palliative care, and followed by the clinic (denominator). For each drug included on the PIMs dashboard, there are associated business rules that define when medication use is flagged as potentially inappropriate; these same criteria will be applied in this trial. For example, use of a first or second generation anti-psychotic drug is flagged as potentially inappropriate unless there is a diagnosis of schizophrenia or bipolar disorder. These criteria had previously been determined by VIONE's Subject Matter Expert group, which provides VIONE with guidance on translating deprescribing criteria into the most practical and appropriate rules for use on the dashboard. Altogether, the following AGS Beers medications from the PIMs dashboard will be included in the analysis: anticholinergics, antipsychotics, aspirin, benzodiazepines, long-acting sulfonylureas, muscle relaxants, NSAIDs, proton pump inhibitors (PPIs), sliding scale insulin, and Z-drugs.

For *DOAC safety*, the outcome will be the proportion of patients with potentially inappropriate prescribing out of those using DOACs, as measured by "flags" (e.g., potential mis-dosing based on renal function and other indicators) on the DOAC dashboard. The DOAC flagging system is based on FDA indications and has been in clinical use since 2018. Components of the outcome include inappropriate dosing for the given indication and use of DOACs in contraindicated settings (such as valve replacements).

For *first-line treatment for insomnia*, the outcome will be the proportion of patients with a new prescription for a sedative-hypnotic medication who have not had CBTI in the prior 12 months out of all primary care patients actively following with the clinic and are not in hospice/palliative care.

For all three trials, medication use (yes/no) and possession of active prescription for each month will be determined using exposure days based on supply days, and use will be determined by the exposure status on day 1 of each month. We will also do sensitivity analyses based on the criteria of use anytime during the month as well as PIMs defined to medications used chronically, for example, greater than 90 of the 180 prior days.

For each trial we will first compare demographic characteristics (age, sex, and race) of patients at risk of potentially inappropriate medications in the first month of implementation between the two arms. We will then obtain, for each trial by arm, crude monthly percentages (along with the corresponding 95% confidence intervals) of potentially inappropriate medications, averaged across clinics randomized to each arm and weighted by clinic-month size. For each trial, we will plot the monthly clinic level percentages over the follow-up 13-36 months to graphically assess if the difference between the two arms can be meaningfully summarized across the three trials with the unified outcome. If we find, for example, that trends between-arms over post-implementation months differ notably across the three trials, unified results comparing AD+LEAP vs. AD arm across trials may not be meaningful, and we will only conduct analyses separately by each trial.

For comparison between arms, we will use generalized estimating equations (GEE) with clinic level monthly percent of potentially inappropriate medications among patients at risk during post implementation period (months 13 to 36) as the dependent variable. The model will include indicators of two trials with one trial as the referent category to account for differing underlying levels of inappropriate medication use across trials. The model will also include follow-up time in months and the LEAP+AD arm indicator with AD as the referent category and will adjust for serial correlation within clinic over time. We will also include time by arm interaction to assess if the magnitude of the difference between LEAP+AD vs. AD changes over time. If the interaction is significant, we will estimate between-arm difference at 18 months as well as at 2- and 3-years separately based on the model with the interaction term. On the other hand, if the interaction is not significant, this would indicate between-arm difference not to differ at the three follow-up times of interest (18, 24, and 36 months), and thus we will drop the interaction term and the parameter estimate of the LEAP+AD arm indicator will be used to estimate the time-averaged difference in percentage of patients with inappropriate medications during post-implementation period in clinics randomized to LEAP+AD compared to clinics randomized to AD.

If we find notable baseline demographic difference between arms within trials, we will use a generalized linear mixed model (GLMM) with logit link to estimate the between-arm difference while adjusting for baseline age, sex, and race difference with monthly person level response (yes/no) data from post-implementation period of months 13 to 36. In addition to time, AD+LEAP indicator and trial type indicators as predictors, the GLMM model using patient level data will include patient age, sex, race, and random intercepts for patients nested within clinic to adjust for potential correlation within clinics and serial correlation over time. The parameter estimate for the LEAP+AD arm indicator will be used to estimate the time-averaged odds of inappropriate medication use during the post-implementation period for patients in clinics randomized to LEAP+AD compared to the odds of the same patients if their clinics were randomized to AD. Although the GEE and GLMM models give different summary estimates with different interpretations, the GLMM model allows for adjusting for patient characteristics, and a consistent substantive conclusion will assure us of the evidence for the effect of LEAP when added to AD. Similar to the GEE model, we will test if the odds ratio of LEAP+AD vs. AD changes over time by including time by arm interaction term, and if the interaction term is significant, we will obtain adjusted ORs associated with LEAP+AD compared to AD at 18 months, 2-years, and 3-years.

For each trial we will also compare AD and AD+LEAP to usual care controls. To do this, we will perform a non-randomized secondary analysis for each trial. The analysis will have the same primary outcome variable and use the same generalized linear mixed model (GLMM) with logit link. The primary control group will be all non-participating sites. We will also use a secondary analysis, where for each intervention site we will have two control sites that are matched on clinic size (within 50%), pre-intervention outcome rate (within 30 rankings of all sites), and region of the country. These analyses will adjust for the clinic-level variables clinic size, intervention outcome rate, region of the country and the patient-level variables age, sex, and race.

Aim 2: Secondary Outcomes and Analyses

Secondary outcomes for VIONE will be the prevalence of potentially inappropriate use of PPIs; the prevalence of potentially inappropriate use of aspirin; and the prevalence of potentially inappropriate use of CNS active medications (muscle relaxants, anti-psychotics, Z-drugs, and

benzodiazepines) or anticholinergic drugs; number of inappropriate medications at a patient level; monthly medication costs for all drugs, without regard to appropriateness; and number of pharmacist medication reviews.

Secondary outcomes for the DOAC trial will be the sub-components of the “flags” on the dashboard. These include potential mis-dosing, potential medication interactions, or concern for nonadherence. This follows the organizational structure of both the presentation of the flags on the dashboard and the key messages provided to the academic detailing and LEAP teams. Process outcomes will be how often the provider uses the dashboard and rates of new DOAC starts compared to warfarin starts. These outcomes will be kept in alignment with our other work using the dashboard [4].

In stand-alone analyses of the CBTI trial, the primary outcome will be the prevalence of any CBTI receipt among primary care patients actively following with the clinic who are not in hospice/palliative care.

Analyses of secondary outcomes such as percent of potentially inappropriate use of PPI or mean number of CBTI sessions at each clinic month will be similar to that of the primary outcome using the GEE model accounting for correlation over time. We will also conduct separate analyses by trial with the dependent variables that are unique to each trial. For example, for the polypharmacy trial, secondary outcome of interest is count of medications flagged as inappropriate based on Beers’ criteria [3]. We will compare monthly rates of Beers’ list medication use between implementation strategies using generalized linear mixed models with log link.

Aim 3: Exploration of Potential Predictors of Clinical Outcomes

Our process evaluation will follow a multi-phase concurrent nested mixed methods design [5]. This design has three purposes: 1) help prepare all stakeholders and participants prior to the start of each trial; 2) monitor progress of implementation; and 3) explain summative findings. Overall priority is placed on quantitative methods that guide the trials, while qualitative methods are embedded or “nested” within conduct of the trials.

Employee behavior and experience measures will be collected via five scales as listed in Table 1. Surveys will be administered via online link within invitation emails; administration will occur at baseline and 12-months post-baseline; satisfaction will be elicited at the end of each intervention (upon completion of the 6-month “core” LEAP program for LEAP team members and at the end of each AD visit for AD participants). Descriptive statistics will be generated and tests for differences across implementation strategy arms will be conducted using mixed models to account for within-clinic correlation.

Qualitative data will be collected prior to and 18-months following baseline via semi-structured interviews (virtual by telephone or conferencing software (e.g., MS Teams platform)). A purposive sample of key people (clinic leaders, supervisors, providers, and staff) at each clinic will be invited to participate so we can better understand the context in which the implementation strategies are/were deployed. The interview guides and qualitative analyses will be guided by the CFIR to identify potential and actual barriers and facilitators [6–8]. Principles embedded within the DSF will guide exploration of the degree of engagement in quality improvement and teamwork [9]. Prior to implementation, this information will help inform the work of the academic detailers and LEAP Coaches; post-

implementation, this information will help to explain quantitative findings within and across the trials. Interviews will be audio recorded and transcribed verbatim. Pre-implementation, interviews will focus on collecting practical information using a rapid analysis approach [10,11] to help tailor and adapt implementation for each participating clinic. Post-implementation, qualitative analyses will seek insights on what kinds of improvements were made, barriers and facilitators to making improvements, reflections on/satisfaction with participation in AD/LEAP and explore *relationships* between determinants, participants, and key stakeholders and how these may lead to building coalitions of support [12,13]. We will combine qualitative findings with quantitative measures from Aims 1 and 3 to help explain changes (or lack of) over time.

Our process evaluation will rely on quantitative and qualitative data sources. Fidelity to each implementation strategy will be tracked by interventionists (the detailers and LEAP coaches) completing a mixed-methods self-assessment tool after each interaction (a coaching session for LEAP, detailing contact for AD). These assessments will be used to guide coach-supervisor and peer reflections on improvements, problem-solving, and mitigating barriers and amplifying facilitators of improvement efforts. We will also track participation by participants (individuals scheduled for detailing and/or LEAP team members) and completed assignments by LEAP teams. The Academic Detailer and LEAP coaches will enter notes for each interaction into a tracking system for each strategy. This data will be combined with pre-implementation and 18-month semi-structured interview data for further insights into barriers, facilitators, and problem-solving approaches used by LEAP coaches and detailers. Quantitative and qualitative data will be combined at the analysis or interpretation phase.

Economic Evaluation

We will use a micro-costing method [14,15] to determine the costs to deliver LEAP and academic detailing (AD). The LEAP coaches and academic detailers developed a list of the activities they will perform for each participating site. Depending on the specific activity, they determined the best way to record the time spent on each activity—e.g., logging the start and stop time each time the activity takes place vs. setting an estimated average time for activities that take approximately the same amount of time for each incidence (such as recurring meetings, responding to quick queries via e-mail, meeting preparation, etc.). In the latter case, the coaches and detailers simply record the occurrence of the activity, which is then assigned the estimated time. The coaches and detailers will log times for each activity, categorized by participating site, in a time tracking database. Using data from this database, we will calculate the average time required for each activity and apply this to the number of times it takes place over the course of performing the implementation strategy at a site. These data can then be used to determine an estimated total time required to perform the implementation strategy (LEAP or AD) at a site, which, combined with the hourly cost of the LEAP coach or detailer, can be used to calculate the total cost of employing the strategy at a site.

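### Does an algorithm described only as sensitive undermine the CBTI trial's any-CBTI outcome?

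*Combined protocol and SAP*

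**What the plan says.** The relevant statements are spread over four places in the Combined protocol and SAP.

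- **List of changes, CBTI sessions.** After further testing, "we found the algorithm to be adequately sensitive to detecting" any CBTI, while session counts were inaccurate. The example offered for the counts is that "CBTI could often be mentioned in the context of a referral or some other ongoing treatment". The mean-sessions outcome was therefore dropped. No sensitivity value, specificity or predictive value is given.
- **List of changes, referrals.** At several sites a referral could not be told apart from other communication, so "we did not have sites collect referral criteria", and the referral outcome was dropped as well.
- **Table 1, CBTI trial.** The source for prevalence of any CBTI receipt is "CBTI note templates completed by CBTI therapists". No algorithm is mentioned.
- **Aims 1 and 2.** When the CBTI trial is analysed alone, "the primary outcome will be the prevalence of any CBTI receipt among primary care patients" under active follow-up and outside hospice or palliative care. Analyses of secondary outcomes "will be similar to that of the primary outcome using the GEE model accounting for correlation over time", and the primary GEE model estimates a "time-averaged difference in percentage of patients with inappropriate medications during post-implementation period". The insomnia component of the pooled outcome counts new sedative-hypnotic prescriptions without CBTI in the preceding 12 months. The planned sensitivity analyses vary the definition of medication exposure only.

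**The concern.** Sensitivity is the share of treated patients who are found. It does not limit the number of untreated patients who are wrongly flagged. The sponsor accepts that referral mentions spoil session counts. The same mention, in the record of a patient who never attended, could also produce a false any-CBTI hit. With referral criteria not collected, the documents describe no site-level marker for removing such hits. Nor do they say how the algorithm relates to the templates in Table 1.

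If LEAP made referral mentions more frequent in its arm, extra referral could be reported as extra treatment in the outcome that matters most for the CBTI trial on its own. A smaller effect could reach the pooled result through the prior-12-month CBTI clause.

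**Working it through.** The documents state no accuracy figure and no CBTI prevalence, so there is no figure to reproduce. Every rate below is an assumption.

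**1. Which source governs.** Table 1 assigns any-CBTI receipt to therapist-completed templates. The list of changes records departures from the plan and includes none for that source. An analyst who follows the document counts templates. An algorithm that reads only those templates also fits both places.

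**2. Size if the algorithm is used and reads more widely.** With true prevalence p, sensitivity Se and false-hit rate g among untreated patients:

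observed = p × Se + (1 − p) × g

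*No true effect, p = 0.5%, Se = 1:*
- g = 0.2%: 0.5% + 99.5% × 0.2% = 0.6990%
- g = 0.3%: 0.5% + 99.5% × 0.3% = 0.7985%
- 0.2% in both arms: difference 0. 0.2% versus 0.3%: +0.0995 points. Reversed: −0.0995 points.

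*True gain of 0.25 points (0.5% versus 0.75%), Se = 1:*
- g = 0.2% in both arms: 0.6990% versus 0.75% + 99.25% × 0.2% = 0.9485%, difference 0.2495
- g = 0.2% versus 0.3%: 0.6990% versus 1.0478%, difference 0.349

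*A harsher assumption, no true effect, p = 2%, Se = 0.90, g = 1% versus 2%:* 1.8% + 0.98% = 2.78% versus 1.8% + 1.96% = 3.76%, +0.98 points.

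With equal error in both arms, a true difference is multiplied by (Se − g). At Se = 1 and g = 0.2% that factor is 0.998, so on the percentage-difference scale of the GEE the loss is negligible. Material bias needs error that differs by arm.

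**3. False hits are not the only route.** With no true effect and equal g, sensitivity of 80% versus 90% gives p × 0.10: 0.05 points at p = 0.5% and 0.20 points at p = 2%.

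**4. Would a template-only count be safer?** Incomplete templates act like reduced sensitivity. Completeness of 80% versus 90% with no true effect gives 0.05, 0.10 and 0.20 points at p = 0.5%, 1% and 2%. This equals the effect of a 0.1-point false-hit gap when 0.10p = 0.001(1 − p), that is p = 0.001/0.101 ≈ 1%. Above that prevalence the template count is the more exposed of the two.

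**5. Would a decision rule help?** Suppose the algorithm result were distrusted whenever the template count shrank the difference by half or more. Take the true gain of 0.25 points with g = 0.2% versus 0.3%, so the algorithm shows 0.349. With template completeness of 90% under AD and 80% under LEAP+AD, the template count shows 0.75% × 0.80 − 0.5% × 0.90 = 0.60% − 0.45% = 0.150. The shrinkage is 1 − 0.150/0.349 = 57%, and the rule would set aside a real effect.

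**6. Reach into the pooled outcome.** This applies only if the algorithm feeds the prior-12-month clause. With new starts in a share s of patients, 5% of them with true prior CBTI, and false hits among the rest of 5% versus 10%, the clinic percentage moves by −s × 0.95 × 0.05: −0.024 points at s = 0.5% and −0.095 at s = 2%. At an assumed one-third weight this is −0.008 to −0.032 points pooled. Adjustment for "the level of potentially inappropriate medications (PIMs) in the pre-period" may absorb the stable part of any clinic-level error.

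**The case for a change.** The best argument for acting is that hits from referral mentions sit awkwardly with a search confined to completed treatment templates, which hints at a wider search. LEAP adds quality-improvement work in one arm only, so differential mention is plausible. The referral outcome that might have exposed it is gone, and a second count looks cheap.

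Part of this stands. Neither the list of changes nor Table 1 says whether the algorithm reads only the templates, and specificity for any CBTI is not reported.

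The rest is weaker. The referral example is attached to session counts, and extending it to any CBTI is an inference. No section describes what LEAP teams in the CBTI trial work on, and both arms receive academic detailing, so even the direction of a differential is conjecture. The dropped referral item concerned where sites record referrals; it does not show that the algorithm cannot exclude referral text. Nothing shows that templates can be counted separately from the algorithm, so the low cost is also assumed. Analysing every new sedative-hypnotic start without the CBTI clause would remove the element that defines the insomnia outcome, and would leave any-CBTI receipt untested. Finally, the document is dated 09/24/2025 and speaks of arm differences as already modelled, so a rule added now might not be prospective.

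**Conclusion.** The concern does not call for a change to the plan. What is missing is a line of description, and Table 1 already gives analysts a sensible way to fill it: count therapist-completed templates. The natural place to name the source used, and any specificity or predictive value that the completed testing yields, is the report of results.

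Bias from referral mentions depends on four links that the documents do not show: the algorithm supplies any-CBTI receipt, it searches beyond the templates, it flags untreated patients, and it does so at different rates by arm. If all four held, the spurious difference would be (1 − p) times the gap in false-hit rates, given equal sensitivity in both arms. That is about 0.10 points for a 0.1-point gap and 0.98 points for a 1-point gap at 2% prevalence. The documents settle neither its size nor its direction. The pooled effect is at most about 0.03 points on the rates assumed above. The extra analyses one might add carry errors of similar size under equally plausible assumptions, so no gain from them is demonstrated.

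### Clinic type is a possible randomisation stratum but is in no between-arm model; where it was used and is prognostic, standard errors are too large

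*Combined protocol and SAP*

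**What the plan says.** The Clinic Randomization section randomises clinics separately within each of the three trials to LEAP+AD or AD alone. It allows allocation to be "stratified further by clinic type (medical center, community clinic, or Community Living Center) if needed to ensure partial balance between arms". The stated purpose is balance on "potential confounders associated with culture and complexities associated with clinic location". There is no criterion for when the extra stratification is needed, and nothing says in which trials, if any, it was applied.

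The between-arm models are these:

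- **Pooled GEE (Aim 1).** "The model will include indicators of two trials with one trial as the referent category". In addition, "The model will also include follow-up time in months and the LEAP+AD arm indicator with AD as the referent category". A time-by-arm interaction and an adjustment for serial correlation complete the model.
- **Patient-level GLMM (Aim 1, if demographics differ notably between arms).** Besides time, arm and trial, it "will include patient age, sex, race, and random intercepts for patients nested within clinic".
- **Secondary outcomes (Aim 2).** A GEE like the primary one, and a mixed model with log link for counts of flagged medications.
- **Model reported on the cover page.** The arm difference was modelled as a single outcome, "adjusting for the evidence-based practice (EBP) and the level of potentially inappropriate medications (PIMs) in the pre-period".

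Clinic type is in none of them. Trial is in the pooled GEE, the GLMM and, as EBP, the cover-page model.

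**The concern.** Restricting the randomisation on a prognostic factor removes that factor's contribution to the variability of the arm difference. A model that omits the factor still counts this contribution as noise between clinics. The reported standard error is then larger than the true sampling variability, the interval is too wide, and the test rejects less often than its nominal level. Random clinic intercepts or a working correlation over time do not repair this, because the variance due to type stays in the between-clinic component.

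What is at stake is power. In a cluster trial the number of clinics limits precision, and clinic type is known for every clinic before randomisation. The plan is also uneven: it has a response to imbalance in patient age, sex and race, but none to imbalance in the one clinic-level factor that it names for stratification.

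**Working it through.** **Inputs.** The documents give no number of clinics, intracluster correlation, power or effect size, and no alpha for the arm test, so there is no stated figure to reproduce. Everything below rests on assumptions: a two-sided 5% test; 80% power for the type-adjusted model; and a share R² of within-trial between-clinic variance explained by clinic type.

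**Case 1: type used to stratify, no pre-period term (the planned GEE).** Let s be the standard error reported without type. The true standard deviation of the estimate is s·√(1−R²). Then:

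- Standard error ratio (reported to true) = 1/√(1−R²)
- True size = 2·[1 − Φ(1.96/√(1−R²))]
- Power = Φ(1.96 + 0.8416 − 1.96/√(1−R²))

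| R² (assumed) | SE ratio | True size | Power |
|---|---|---|---|
| 0 | 1.00 | 5.0% | 80% |
| 0.10 | 1.05 | 3.9% | 77% |
| 0.20 | 1.12 | 2.8% | 73% |
| 0.30 | 1.20 | 1.9% | 68% |

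For example, at R² = 0.30 the ratio is 1/√0.70 = 1.195. The power argument is 2.8016 − 1.96 × 1.195 = 0.459, and Φ(0.459) = 0.677.

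A simulation of clinic-level means agrees (three trials, 12 clinics each, two types per trial, 1:1 allocation, 2,000 runs). At R² = 0.30 and stratified allocation, the reported standard error without type was 0.336 against a true standard deviation of 0.271, with size 1.9%. With type in the model it was 0.276 against 0.271, with size 4.3%.

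**Case 2: type not used to stratify.** In the same simulation at R² = 0.30, the model without type had standard error 0.334 against true standard deviation 0.339 and size 5.2%. The interval matches the design. Adding type lowered the true standard deviation to 0.286, so precision was available but there was no error.

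**Case 3: type used to stratify, pre-period level in the model (the cover-page analysis).** The comparison is of reported standard errors without and with type, at an assumed pre-post correlation:

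- Correlation 0.8, R² = 0.30: 0.171/0.169 = 1.01, about 1%.
- Correlation 0.5, R² = 0.30: 0.256/0.244 = 1.05, about 5%.
- Correlation 0.5, R² = 0.50: 0.221/0.205 = 1.08, about 8%.

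A clinic-type difference that is stable over time is already carried largely by the pre-period level, so little is left for type to explain. In the last two settings the standard error reported without type was also close to the true standard deviation (0.256 against 0.259, and 0.221 against 0.216).

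**The case against.** The strongest reply is that the harm is conditional twice over. It needs clinic type to have been a stratum, and it needs type to predict the outcome within trial. The documents establish neither. A reader might infer that precision has in fact been lost and that the trial's intervals do not match its design. The text does not support this: the stratification is optional, no variance share is given, and the certain stratum, trial, is modelled. If type was not a stratum, the intervals are valid as they stand.

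A reader might also infer a risk of false positives or bias. Neither follows. Under randomisation the omission does not bias the estimate, and any error in the interval is in the conservative direction. Nor does the plan call clinic type itself a confounder; it uses type as a proxy for features of location and culture.

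A larger power loss (76%, 71% and 65%) comes from computing Φ(2.80/ratio − 1.96), where ratio is the standard error ratio above. That formula suits unstratified allocation. It does not apply where stratification has already reduced the true variability.

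The cover-page adjustment is a fair defence for the PIM outcome, and most of it stands. It does not settle Aim 2. Medication costs, pharmacist reviews and CBTI receipt are different outcomes, and pre-period PIM level need not capture clinic-type differences in them. Because the plan says that secondary analyses resemble the primary one, the adjustment may have carried over; the documents do not say. It would therefore go too far to claim that the loss is greatest for Aim 2.

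Finally, type nested in trial in every model could add up to six parameters (two per trial in three trials) when the number of clinics is unknown. That objection stands and limits the remedy.

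**Conclusion.** The point holds in conditional form. Clinic type is a possible stratum with no stated rule for its use, and no between-arm model contains it. Where it was used and is prognostic, a model without a pre-period term reports a standard error 5% to 20% too large for assumed type shares of 10% to 30%, with true size between 3.9% and 1.9% and power between about 77% and 68% instead of 80%. For the PIM outcome with the cover-page adjustment, the remaining effect on the reported standard error is about 1% (type share 30%, pre-post correlation 0.8), rising to about 5–8% if that correlation is 0.5 and the type share is 30–50%. For Aim 2 outcomes the larger range remains possible, because it is not stated whether a pre-period term applies. If type does not predict the outcome, nothing is lost. The type shares, correlations, alpha and numbers of clinics are all assumptions.

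**What to change.** - State in which trials clinic type was used to stratify.
- In those trials, include clinic type as a fixed effect in the pooled, single-trial and secondary between-arm models, collapsing sparse levels. Use the same strata in any permutation test.
- Where type was not a stratum, or where the analysis has already been run (the cover page reports the PIM modelling in the past tense), report the type-adjusted model as a labelled sensitivity analysis beside the main result.
- State whether the pre-period adjustment applies to the Aim 2 outcomes.

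The cost is a few degrees of freedom, some added text in the analysis plan and a rerun. No new data should be needed, since clinic type had to be known to be available for stratification.
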